Field of view is one of the most important hardware tools that must be determined carefully to get more reliable and accurate measurements (**Abdelkarim, 2019**).

FOV must be determined according to the needs of the case.

Small FOV devices range normally from 5 to 10 cm, which give a 3D view of a single tooth unit and its surrounding anatomy. They are used for individual tooth assessment (e.g; impacted teeth, root morphology, supernumeraries, sites for placement of dental implants, and temporary anchorage devices). Medium FOV provides single jaw anatomy, whereas the maxillomandibular FOV gives the clinician an understanding of two-jaw anatomy, temporomandibular joint (TMJ), and occlusion. They are used for more information on facial asymmetries, bilateral TMJ evaluations and occlusal relationships.

In addition, Large or craniofacial FOVs include the cranial base, cranium and all associated structures. The large FOVs involve most of the whole head which help clinicians to assess relationships between skeletal bases, between teeth and skeletal bases, and also can be significant for anomalies in patients requiring orthognathic surgery or those with craniofacial anomalies (**Kau and Ortho, 2014**).

In a study done by **Shokri et al**, to evaluate the effect of exposure parameters of milliampere (mA) and field of view (FOV) of CBCT image on a metal artifact of dental implants by using of 27 bone blocks with different densities (nine were type 1, nine were types 2 and 3, and nine were type 4). These blocks were placed in mandibular wax models. Then scanned after drilling and implant placement using Cranex3D imaging system with a $4 \times 6 \text{ cm}^2$ and $6 \times 8 \text{ cm}^2$ FOV and 4 and 10 mA. Gray value of the bone blocks was

recorded before and after placement of implants. And the result was that the amount of artifacts was lower in small FOV compared to large FOV ($P < 0.05$). Change of mA had no effect on metal artifacts ($P > 0.05$). Artifacts in type 4 bone were greater than in other bone types ($P < 0.05$). Difference between type 1 and types 2 and 3 was not significant ($P > 0.05$).

Study objectives and hypotheses:

Study objectives:

The objective of this study will be the evaluation of the effect of variation of the exposure parameters FOV & mA on the produced metallic artifact induced by dental implants that affect the CBCT image using linear measurements of dental implant dimensions.

Study hypotheses:

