Is the variation of Field of view (FOV) and milliamperere (mA) can affect the CBCT image quality with metal artifacts?

III. Methods

A) Samples, intervention and outcomes

7. Calculated sample size

A power analysis was designed to have adequate power to apply a statistical test of the null hypothesis that there is no difference between tested groups. By adopting an alpha level of (0.05) a beta of (0.2) i.e., power=80% and an effect size (f) of (0.38) calculated based on the results of a previous study¹; the predicted sample size (n) was a total of (80) cases. Sample size calculation was performed using G*Power version 3.1.9.7²

8. Description of study sample

- 4 dry human mandibles will be obtained from faculty of medicine from Cairo University.
 - Layers of dental wax for soft tissue stimulation from dental store of El-Kasr El-Einy, faculty of dentistry, Cairo University.
 - 8 dental implants will be obtained from Roots Company.
 - Each dry human mandible with implant will be scanned in the Oral and Maxillofacial Radiology Department, Faculty Dentistry, Cairo University using CBCT machine Planmeca ProMax® 3D Mid.
 - Produced CBCT images will be analyzed by using Romexis ® software (planmeca Helsinki-Finland) for measuring dental implant dimensions (length and width) using linear measurements on software and real measurements of dental implants as a reference standard.
-

9. Intervention for each group

- Each mandible will be prepared and drilled for implant placement at the middle of the bone at the area of interest
- Two layers of wax will be applied over them for soft tissue stimulation.
- Then each mandible will be scanned by using CBCT machine Planmeca ProMax® 3D Mid in the Oral and Maxillofacial Radiology Department, Faculty Dentistry, Cairo University 4 times with 4 different protocols of FOV (40 × 50 mm & 100 × 60 mm) and mA (8 and 10) by the following:
 - First:
 - mA 8 and FOV 40 × 50
 - mA 8 and FOV 100 × 60
 - mA 10 and FOV 40 × 50
 - mA 10 and FOV 100 × 60
 - Second:
 - mA 8 and FOV 40 × 50
 - mA 8 and FOV 100 × 60
 - mA 10 and FOV 40 × 50
 - mA 10 and FOV 100 × 60
 - Third:
 - mA 8 and FOV 40 × 50
 - mA 8 and FOV 100 × 60
 - mA 10 and FOV 40 × 50
 - mA 10 and FOV 100 × 60
 - Fourth:
 - mA 8 and FOV 40 × 50
 - mA 8 and FOV 100 × 60
 - mA 10 and FOV 40 × 50
 - mA 10 and FOV 100 × 60

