- Each CBCT image Produced will be analyzed for metal artifact by using Romexis ® software (planmeca Helsinki-Finland) for measuring dental implant dimensions (length and width) using linear measurements

10. Outcomes

The primary outcome of this study will be the assessment of Implants dimensions measurements that will be measured by using linear measurement on Romexis® software (Planmeca-Helsinki-Finland) for each scan to evaluate the effect of FOV and mA on artifacts induced by dental implants.

Prioritization of Outcome	Method of Measurement	Unit of Measurement
Assessment of implants dimensions measurements accuracy	Linear measurements	Millimetres (mm)

B) Assignment to intervention

The randomization will be applicable.

11. Sequence generation

Mechanism used to implement the random allocation sequence is that mandibles will be sequentially numbered.

12. Allocation concealment

Opaque sealed envelopes will be used to conceal the sequence until intervention is assigned.

12. Implementation:

The main supervisor will be responsible for the random allocation sequence and enrolling mandibles, but the co-supervisor and the researcher will be responsible for assignment for intervention.

C) Blinding

14. Blinding

The Co-supervisor and investigator will be blinded.

D) Statistical methods

Handling of numerical/ quantitative variables:

Numerical data will be explored for normality by checking the data distribution, calculating the mean and median values and using Kolmogorov-Smirnov and Shapiro-Wilk tests. If the data was found to be normally distributed, it will be presented as mean and standard deviation values. If the assumption of normality was found to be violated, the data will be presented as median and range values.

Handling of categorical/ qualitative variables:

Categorical data will be represented as frequency (n) and percentage (%).

Statistical methods:

Categorical data will be represented as frequency (n) and percentage (%) and will be analyzed using chi square test. Numerical data will be explored for normality by checking the data distribution, calculating the mean and median values and using Kolmogorov-Smirnov and Shapiro-Wilk tests. If the data was found to be normally distributed, it will be presented as mean and standard deviation values and one-way ANOVA followed by Tukey's post hoc test will be used for the analysis.

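### No step in the plan hides FOV from whoever measures the images, so the stated blinding does not cover the FOV comparison

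*Combined protocol and SAP*

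**What the plan says.** The blinding statement in section 14 is complete in one sentence: "The Co-supervisor and investigator will be blinded". It does not say to what these people are blinded, at which stage, or how. The protocol mentions no coded files, no common cropped region and no independent reader.

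Section 9 (Intervention for each group) has each mandible scanned "4 times with 4 different protocols of FOV (40 × 50 mm & 100 × 60 mm) and mA (8 and 10", the last two figures being the mA levels. Section 10 (Outcomes) says implant dimensions will be "measured by using linear measurement on Romexis® software (Planmeca-Helsinki-Finland) for each scan to evaluate the effect of FOV and mA". The person who takes the measurement, the view used and the way points are placed are not given. Section 8 (Description of study sample) takes the "real measurements of dental implants as a reference standard".

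The Review of literature summarises an earlier study of the same two factors. It found that "the amount of artifacts was lower in small FOV compared to large FOV" and that changing mA made no difference.

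**The concern.** File codes and sealed envelopes hide labels and allocation. They do not hide what the image shows. If the reader sees the whole reconstructed volume, its extent gives away the field. Masking would then fail for one of the two study factors, and that is the factor for which the protocol cites a previous positive finding.

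At stake is the interpretation of an FOV difference. The endpoint is a distance read in viewer software. If a person sets the end points, knowledge of the field can influence where they go. A systematic influence of this kind is not averaged out by further readings from the same reader. The final report would also claim blinding that the images defeat for this comparison.

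**Working it through.** The plan gives no figure on masking, so there is none to reproduce. The check sets its statements side by side and counts the contrasts affected.

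**1. Can the field be recognised from the image?** Inputs: the nominal field sizes in section 9.

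- First dimension: 100 / 40 = 2.5 times.
- Second dimension: 60 / 50 = 1.2 times.
- Product of the two: (100 × 60) / (40 × 50) = 6000 / 2000 = 3 times.

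A threefold difference in nominal area is visible in an uncropped volume. The two mA levels (8 and 10) are used with both fields, so extent carries no information about mA.

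**2. Does any planned step remove that cue?** Sections 11 and 12 cover numbering of mandibles, envelopes and who allocates. All of these act before scanning. Section 14 names people and no procedure. Section 10 and the last item of section 9 describe measurement on each scan with no preparation of the images. No step removes the cue.

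**3. Which comparisons are affected?** Label the protocols A (8 mA, 40 × 50), B (8 mA, 100 × 60), C (10 mA, 40 × 50) and D (10 mA, 100 × 60). Number of pairs: 4 × 3 / 2 = 6.

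| Pair | FOV differs | mA differs |
|---|---|---|
| A–B | yes | no |
| A–C | no | yes |
| A–D | yes | yes |
| B–C | yes | yes |
| B–D | no | yes |
| C–D | yes | no |

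Four of the six pairs differ in FOV. The overall one-way ANOVA and four of the six Tukey comparisons in D) Statistical methods therefore include an FOV contrast that is not masked. Only A–C and B–D are free of this cue.

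**4. Is there an expectation for the reader to follow?** The cited study reports less artifact with the smaller field. It measured gray values, with fields of 4 × 6 and 6 × 8 cm, and not implant length or width. It gives a reader a reason to expect the smaller field to perform better. It gives no direction for a shift in millimetres. The most it suggests is a smaller error against the reference dimensions.

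**5. How large could the bias be?** The plan gives no standard deviation, voxel size or reader error for the measurement. Neither a shift in millimetres nor a false-positive rate can be calculated without inventing inputs, so none is offered.

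**6. How much work is the fix?** Inputs: 4 mandibles and 8 implants (section 8), 4 protocols (section 9). Scans: 4 × 4 = 16. Implants per mandible, if evenly divided: 8 / 4 = 2. Crops: at most 16 × 2 = 32, if both implants of a mandible fall in every scan. Implant positions are not stated, so 32 is conditional.

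**The case against.** The strongest reply is that this is a gap in description. The protocol does not say that the reader views the full volume, nor that points are set by hand. A reader working on a zoomed cross-section might see little of the extent. That stands: both features are inferred from linear measurement in the software. What remains is that the plan claims blinding and contains no step that would deliver it for FOV.

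Four stronger readings are tempting and are not supported.

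- A reader might infer that blinding to FOV is impossible. It is not: coding alone fails, but identical crops would hide extent.
- A reader might take the Review of literature as proof that the two fields look different, since it describes small fields as ones "which give a 3D view of a single tooth unit and its surrounding anatomy" and adds that "Medium FOV provides single jaw anatomy". The same section puts small fields at 5 to 10 cm. The 100 × 60 mm field is 10 × 6 cm and falls within that range, so these categories do not separate the two fields. The nominal dimensions do.
- A reader might infer that the earlier study predicts a shift in measured length. It measured gray values, and this protocol's own hypothesis has no direction.
- A reader might infer that the physical reference removes the problem. It fixes the true value but does not protect the placement of points, and a reader who knows the true size could be drawn towards it.

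It can also be said that the better documented fault is one of roles: section 12 (Implementation) states that "the co-supervisor and the researcher will be responsible for assignment for intervention", while section 14 counts the co-supervisor as blinded. Those statements must be reconciled. Doing so would still leave FOV visible to anyone who opens an uncropped volume.

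**Conclusion.** The point holds in a limited form and should be settled before any image is measured. As written, the plan does not mask FOV from the person who measures, and coding the files would not change that. The affected contrasts are four of six protocol pairs.

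The conclusion rests on two assumptions: that the reader sees an uncropped volume, and, for bias to follow, that points are placed manually. Both are likely from the wording of the outcome but neither is stated. The documents do not show that bias will occur, and its size cannot be derived from them. The supportable conclusion is that an FOV difference could not be cleanly separated from reader expectation, and that the blinding claim is too broad for this factor.

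**What to change.** Before reading starts, produce from every scan the same cropped region around each implant, small enough to lie within the 40 × 50 mm field. Remove field-size and exposure overlays, display all crops at equal magnification, code them, and have the reader measure only these crops in random order. Add to section 14 who reads, what they are masked to and how. State there that cropping hides extent, and that differences in noise or artifact between fields may still be visible.

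If the software does not allow such crops, amend section 14 to say that the reader is masked to mA only, and report the FOV comparison as unmasked. That wording still requires coded files with exposure information removed.

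The cost is preparation time for 16 scans (up to 32 crops if both implants of a mandible fall in every scan) and a few lines in section 14. No extra scan, specimen or reader is needed for the cropping itself.
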